6.3.3.8 Change in patient resource use (eg, work/school attendance, visits to doctor/hospital)

Change in patient resource use (eg, work/school attendance, visits to doctor/hospital) from baseline will be summarized descriptively.

6.4 Pharmacodynamic analysis

Pharmacodynamic analyses will be conducted using the Safety Analysis Set.

6.4.1 Antithrombin

AT levels and AT lowering (% lowering from baseline) will be summarized descriptively. In addition, mixed model repeated measures (MMRM) analyses will be performed on AT lowering with fixed effects of treatment arm, randomization strata of number of bleeding episodes in the 6 months prior to study entry (≤ 10 vs > 10), randomization strata of hemophilia type (A vs B), visit and baseline AT level. A suitable covariance structure will be chosen to minimize Bayesian information criteria (BIC).

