5.3.1. Discontinuation of Investigational Medicinal Product

The Investigator or designee may discontinue dosing in a patient if the patient:

- Is in significant violation of the protocol
- Is non-adherent to treatment regimen
- Experiences a serious or intolerable AE, a life-threatening bleeding episode, eg, any gastrointestinal hemorrhage or intracranial hemorrhage, or life-threatening thromboembolic event
- Requires a prohibited medication.

The Investigator will confer with the Sponsor or study Medical Monitor before discontinuing dosing in the patient.

Patients (or their guardians) may decide to discontinue IMP.

In general, patients who discontinue IMP dosing for any reason will be encouraged to remain on the study to complete the remaining assessments through the end of study so that their experience is captured in the final analyses. If a patient discontinues dosing due to a serious adverse event (SAE), the SAE should be followed as described in Section 7.5.6. When a patient discontinues IMP dosing, the primary reason must be recorded in the appropriate section of the eCRF. Patients who discontinue IMP but who remain on study may receive treatment consistent with local standard practice for their disease per Investigator judgment, as applicable. Safety will be captured for the entire duration of study for patients who discontinue treatment.

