6.5. Monitoring and Management of Thrombotic Events

Given safety events observed thus far and the possible thrombotic risk associated with fitusiran's AT lowering mechanism, which may be increased with concurrent use of factor replacement products or BPAs, there should be a low threshold to evaluate any signs and symptoms consistent with thrombosis, including symptoms consistent with CVST. Symptoms of thrombosis may include a severe or persistent headache, headache with nausea and vomiting, chest pain/tightness, coughing up blood, trouble breathing, abdominal pain, fainting or loss of consciousness, vision problems, and swelling or pain in the arms or legs.

If signs and symptoms consistent with thrombosis are present, the Investigator should evaluate the patient for thrombosis, including appropriate imaging studies. For the diagnosis of CVST

magnetic resonance imaging venogram (MRV) or computed tomography venogram (CTV) are recommended.[7]

If a patient develops a thrombosis while on fitusiran, AT reversal is recommended in combination with factor or BPA replacement and appropriate anticoagulation. AT reversal should follow labeled product recommendations for the prevention of perioperative thrombosis in patients with AT deficiency, and patient doses individualized to target 80-120% AT activity. The use of plasma derived AT may be preferable to recombinant AT, given its longer half-life. It is recommended that cases of thrombosis are discussed with the study Medical Monitor and Clinical Advisor (see Section 7.5.6.1 for further information regarding Adverse Events of Special Interest).

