8.2.6. Pharmacodynamic Analysis

AT and thrombin levels will be summarized descriptively by scheduled visit. Mixed models repeated measures analyses may be performed as deemed appropriate. Correlation between AT and thrombin levels may be explored.

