4 PATIENT POPULATION

The populations (analysis sets) are defined as follows:

- Intent-to-treat (ITT) Analysis Set: All randomized patients. All by-treatment analyses based on the ITT analysis set will be performed according to the randomized treatment arm. Efficacy Analyses will be conducted using the ITT Analysis Set unless otherwise specified.
- Safety Analysis Set: All patients who received at least 1 dose of study drug or were randomized to on-demand arm. All by-treatment analyses based on the safety analysis set will be according to the actual treatment received. Safety Analyses will be conducted using the Safety Analysis Set unless otherwise specified.
- Per-protocol Analysis Set: All patients in the ITT set who do not have protocol deviations in the following categories:
 - Failure to meet key eligibility criteria, which will be identified prior to database lock.
 - Actual treatment differs from IRS treatment assignment
 - Prophylactic use of factor
 - Other protocol deviations that might significantly affect the completeness, accuracy, and/or reliability of the bleeding data.

The major or critical detail deviations included are as follows.

- The subject is not male and/or is younger than 12 years, but the subject was randomized.
- The subject does not have severe hemophilia A or B without inhibitors as evidence by:
 - A laboratory FVIII level $<1\%$ or FIX level $\leq 2\%$ at Screening.
 - On-demand use of factor concentrate to manage bleeding episodes for at least the last 6 months prior to Screening, or meeting one of the following criteria:
 - Nijmegen-modified Bethesda assay inhibitor titer of <0.6 BU/mL at Screening,
 - No use of bypassing agents to treat bleeding episodes for at least the last 6 months prior to screening
 - No history of immune tolerance induction therapy within the last 3 years prior to Screening,but the subject was randomized.
- The subject does not have a minimum of 6 bleeding episodes requiring factor concentrate treatment within the last 6 months prior to Screening, but the subject was randomized.
- The subject has known co-existing bleeding disorders other than hemophilia A or B, but the subject was randomized.
- The subject currently uses factor concentrates as regularly administered prophylaxis designed to prevent spontaneous bleeding episodes, but subject was randomized.

- The subject's actual treatment differs from randomization group.

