Onset Period	Day 1 to the earlier of Day 28 and the last day of bleeding follow up
Efficacy Period	Day 29 to the earliest of (Day 246, or the last day of bleeding follow up)

Treatment Period	Onset period plus the efficacy period
------------------	---------------------------------------

The last day of bleeding follow up is defined as the deactivation date captured in eDiary.

If a patient does not have bleeding episode data collected after Day 28 due to early study discontinuation, the efficacy period will be from Day 1 to the earlier of date of study discontinuation and the last day of bleeding follow up.

The onset period, efficacy period and treatment period also exclude the period of following intercurrent events to avoid confounding of treatment effect for the primary efficacy analysis based on On-Treatment Strategy.

- After one month (28 days) from fitusiran treatment discontinuation in the fitusiran efficacy period. Excluding bleeding data after one month from fitusiran treatment discontinuation is considered reasonable and adequate considering that fitusiran is dosed monthly and EOS is one month after last dose of fitusiran.
- Perioperative period of major surgery. The perioperative period is defined as the day of the surgery through the final day on which supplemental hemostatic or antithrombotic treatments are administered as part of the perioperative treatment plan.
- Period of minor surgery is defined as the Perioperative period of surgery above or to 72 hours from the end of surgery, whichever is later.
- Period of Antithrombin treatment is defined as the first day of antithrombin treatment through the final day on which antithrombin or other anticoagulant therapies are administered plus 5 half-lives of that specific product.
- After prophylactic treatment with emicizumab, BPA or factor.

The summary statistics for number of patients who are lost-to-follow-up and who had each intercurrent event will be provided.

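### The SAP sets no exclusion for antithrombin values taken during antithrombin-concentrate treatment or well after permanent fitusiran discontinuation, so by default they dilute the reported AT lowering

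*SAP*

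**What the plan says.** SAP 6.4 gives one general rule for pharmacodynamics: "Pharmacodynamic analyses will be conducted using the Safety Analysis Set". SAP section 4 adds that "All by-treatment analyses based on the safety analysis set will be according to the actual treatment received", so a patient who took fitusiran and then stopped stays in the fitusiran column. For antithrombin, SAP 6.4.1 states that "AT levels and AT lowering (% lowering from baseline) will be summarized descriptively" and that "mixed model repeated measures (MMRM) analyses will be performed on AT lowering with fixed effects of treatment arm", together with the two strata, visit and baseline AT. No arm-by-visit term is listed, no visits are named and no values are excluded. Protocol 8.2.6 says only that "AT and thrombin levels will be summarized descriptively by scheduled visit". SAP 6.4.3 correlates AT and thrombin on all same-day pairs.

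The one exclusion among the pharmacodynamic analyses is in SAP 6.4.2. It drops peak thrombin values within 48 hours of factor, bypassing agent or antifibrinolytic. It does not mention antithrombin concentrate and does not apply to AT.

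For bleeding, SAP 6.3 does set such rules. "Period of Antithrombin treatment is defined as the first day of antithrombin treatment through the final day" on which antithrombin or another anticoagulant is given, plus five half-lives of the product, and that period is removed. Time beyond 28 days after fitusiran discontinuation is removed as well. The stated reason is confounding of the treatment effect, and the stated scope is the primary efficacy analysis.

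**The concern.** The protocol foresees both kinds of affected value. When AT reversal is used for thrombosis, Protocol 6.5 describes "patient doses individualized to target 80-120% AT activity". Protocol 6.3.1.2, 6.3.1.3 and 6.6 name further situations in which AT replacement is to be considered, and 6.7 permits AT correction in sepsis. Under Protocol 5.3.1, patients who stop dosing "will be encouraged to remain on the study to complete the remaining assessments through the end of study", and Table 1 samples AT at every visit.

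The analysis windows in SAP 5.10 go by study day, not by time since the last dose. An off-drug or post-concentrate value therefore falls into the same visit row as on-drug values.

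The stated objective is to characterize the pharmacodynamic effect of fitusiran. Antithrombin concentrate acts on bleeding indirectly but on measured AT activity directly, so the reason given in SAP 6.3 applies here with more force. At stake is an accurate description of how far the drug lowers AT and how variable that lowering is.

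**Working it through.** The plan gives no figure on this point to reproduce. The check has a reading of the rules, set out above, and an illustration of size.

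**Inputs from the documents**
- Mean maximum AT reduction at 80 mg: 87% (Protocol 1.2.2.3, Phase 1 Part C, N=6). This is a mean of maxima and serves only as a reference level.
- AT activity targeted with AT reversal: 80-120% (Protocol 6.5).
- Recovery level that ends AT follow-up: about 60% activity (Protocol 7.3.1).
- Fitusiran arm: 80 patients (Protocol 1.3).

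**Assumptions**
- Baseline AT is near 100%. Activity of 80-120% is then a lowering of c = 20 to -20, and 60% activity is c = 40.
- A share f of fitusiran-arm values at a visit is affected. The documents give no f, so a range is shown. With 80 patients, 5% is 4 patients and 10% is 8.
- The SD of lowering is 5 for on-drug values and 10 for affected values.

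**Formulas**
- Mean = (1 - f) × 87 + f × c
- SD = √[(1 - f) × 25 + f × 100 + f(1 - f)(87 - c)²]

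Example, f = 5% and c = 40:
- Mean = 0.95 × 87 + 0.05 × 40 = 84.65.
- SD = √(23.75 + 5 + 0.0475 × 2209) = 11.6.

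| f | Recovered to 60%: mean (SD) | After concentrate, 80% activity: mean (SD) | After concentrate, 120% activity: mean (SD) |
|---|---|---|---|
| 0 | 87.0 (5.0) | 87.0 (5.0) | 87.0 (5.0) |
| 1% | 86.53 (6.9) | 86.33 (8.4) | 85.93 (11.8) |
| 5% | 84.65 (11.6) | 83.65 (15.6) | 81.65 (23.9) |
| 10% | 82.30 (15.2) | 80.30 (20.9) | 76.30 (32.6) |

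**Median.** If all affected values lie below the on-drug median, the new median is the on-drug quantile at (0.5 - f)/(1 - f).
- f = 5%: 0.45/0.95 = 0.474, z = -0.066, a shift of 0.066 × 5 = 0.3 points.
- f = 10%: 0.40/0.90 = 0.444, z = -0.140, a shift of 0.7 points.

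The mean shifts in the recovered case are 2.35 and 4.70 points.

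**Follow-up visit.** SAP 5.10 labels the post-EOS follow-up as Day 281, and SAP 6.4.1 does not say whether the model includes it. Take a plain average over the 11 on-study post-baseline visits at 87% plus a Day 281 value at 40%.
- All patients contribute: (11 × 87 + 40)/12 = 83.1%.
- 10% contribute: (11 × 87 + 0.1 × 40)/11.1 = 86.6%.

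This is simple averaging, not a fitted model. Only fitusiran-arm patients have this visit, so in an additive model its visit term would absorb much of the recovery. The arm contrast would then move less than an arm mean averaged over visits.

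**The case against.** The strongest case on the other side has four parts.

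- **Robust summaries are already planned.** SAP 5.2 requires median, quartiles, minimum and maximum. The median barely moves and an outlying value shows at the extreme. SAP 6.1 and 6.3 also tabulate discontinuations and each intercurrent event. This stands for the descriptive tables. It does not help the repeated-measures model, which works on means, or the correlation.
- **The affected share may be small.** AT reversal is recommended only for thrombosis and otherwise to be considered, and several treated patients would have to be near target at the same scheduled draw. Recovery may be slow. Protocol 4.2 allows 6 months of AT follow-up; if it took that long, a patient would have to stop by about Day 70 (253 - 183) to be at 60% by Day 253. This stands, and the table is an illustration, not a forecast.
- **No conclusion changes.** Every illustrated mean, down to 76.3%, stays above the 75% lowering target in Protocol 1.4. AT is exploratory and outside the testing hierarchy, and the bias works against the drug. This stands and limits the weight of the point.
- **Recovery belongs to the endpoint.** AT activity over time should show washout, and post-EOS values have their own label. This stands for post-EOS values in the by-visit tables. It does not cover early discontinuers whose values share a row with on-drug patients.

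A reader might infer more than the documents support:
- That the sponsor chose to report exogenous antithrombin as drug effect. The SAP is silent, and inclusion is only the default reading.
- That the AT result is needed to explain the bleeding result on the same patient-time. SAP version 2 removed the analysis of bleeding rate by AT lowering (SAP 2.6), so the SAP no longer makes that link.

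**Conclusion.** The gap is real and modest. Followed as written, the plan lets AT values that reflect concentrate or recovery after permanent discontinuation enter the fitusiran-arm AT summaries, the AT model and the AT-thrombin correlation. The same SAP treats those periods as confounding in the primary bleeding analysis.

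The effect is to understate mean lowering and inflate the SD. With 5% of values affected, an 87% mean becomes about 84.7% (recovered to 60%) or 81.7% to 83.7% (after concentrate). With 1% affected it stays at or above 85.9%. These figures rest on the assumed share, a baseline near 100%, and full recovery or full correction in the affected values; the SDs also rest on the assumed spreads.

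The documents do not show that later visits will look like waning effect; that would need an affected share they do not give. Primary and secondary results are untouched.

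**What to change.** Add a rule to SAP 6.4 for the main AT summaries, the AT and peak thrombin repeated-measures models, and the AT-thrombin correlation:

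- Exclude fitusiran-arm values in the antithrombin-treatment period already defined in SAP 6.3.
- Exclude fitusiran-arm values more than 28 days (plus the 7-day visit window) after the last dose in patients who permanently discontinued fitusiran. Do not extend this to doses that were merely missed or withheld; that would go beyond the SAP 6.3 rule and make the result conditional on uninterrupted dosing.
- Leave the post-EOS AT follow-up visit out of the AT and peak thrombin models, and name the visits that are in them.
- Show off-drug values separately by time since the last dose, and keep an all-values table as supportive.

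The cost is SAP wording and a flag built from dosing and concomitant-medication dates already needed for the bleeding analysis. The downside is slightly fewer values at late visits. No data collection or patient management changes.

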1.2.2.3. Summary of Pharmacokinetic and Pharmacodynamic Effects in ALN-AT3SC-001 and ALN-AT3SC-002

Consistent with the intended pharmacological effects, regardless of inhibitor status, fitusiran dose-related reductions in AT activity level have been observed in the clinical studies, and have been associated with increased thrombin generation. In Part C of the Phase 1 study, the mean maximum AT activity level reductions following 3 monthly doses of 0.225, 0.45, 0.9 or 1.8 mg/kg fitusiran were 70% (N=3), 77% (N=3), 77% (N=3), and 89% (N=3), respectively. A fixed dose, 80 mg fitusiran, was also explored in Part C, resulting in a mean maximum AT activity level reduction of 87% (N=6). In Part D of the study, patients with inhibitors were dosed with 50 or 80 mg fitusiran and experienced mean maximum AT activity level reduction of 82% (N=6) and 87% (N=11), respectively. AT reduction was maintained in ALN-AT3SC-002, with mean maximal AT reduction of 83.6% for 50 mg (N=13) and 85.9% for 80 mg (N=21) as of 08 August 2017.

Consistent with the therapeutic hypothesis, increased AT lowering in patients with hemophilia resulted in increased thrombin generation when AT lowering was in the highest quartile (>75%) compared to when AT lowering was in the lowest quartile (<25%). Further, the peak thrombin generation values achieved with AT lowering of >75% were comparable to those in the lower end of the normal range observed in healthy individuals. None of the thrombin generation measurements following >75% AT reduction in hemophilia patients exceeded those seen in healthy males.

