1.4. Dose Rationale

Dose selection was guided by the principle of identifying an optimal dose that is both well-tolerated and efficacious. The fitusiran dose proposed for Phase 3 development was identified using both observed data from ongoing clinical studies, as well as extensive clinical simulations and modeling. The key PD and clinical parameters used to support the dose selection include decreases in AT activity, the most proximate and direct PD effect of fitusiran, as well as increases in thrombin generation and decreases in ABR.

Observed data from Phase 1 and Phase 1/2 studies in patients with hemophilia A and B with or without inhibitors, and PK/PD-modeled data, support selection of a fixed dose of 80 mg for this study, as subcutaneously administered once-monthly.

In observed data from Phase 1 and Phase 1/2 studies, monthly equivalent doses or monthly doses ranging from 0.045 mg/kg to 1.8 mg/kg and fixed doses of 50 mg and 80 mg have been evaluated. A clear dose response trend of increased AT lowering is evident, with approximately 10% to 20% residual AT activity at a dose of 1.8 mg/kg and at fixed doses of 50 mg and 80 mg subcutaneously administered once monthly. These data suggest that the maximum AT lowering achieved as a function of the dose administered reaches an asymptote at $\sim 90\%$ AT lowering and that it is unlikely higher doses will achieve meaningfully greater AT lowering. In addition, both the 50 mg and 80 mg fixed doses produced substantial increases in peak thrombin generation, which approach the lower end of the normal range, but do not exceed the normal range.

Dose-response modeling analyses are supportive of the observed data. A repeated time to event model was used to evaluate the relationship between AT lowering and the anticipated ABR. According to the model, the 80 mg, fixed, once-monthly dose is anticipated to result in near

maximal achievable reduction in ABR, in which the majority of patients may achieve >75% AT lowering, the therapeutic target. Weight was not a significant covariate in the model, suggesting no advantage to weight-based dosing.

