All patients will be treated for a total of 9 months; patients randomized to the fitusiran treatment arm will receive a total of 9 SC injections of fitusiran. Because the full PD effect of fitusiran is not achieved until approximately 28 days after receiving the first dose, efficacy will be assessed during the final 8 months on study (Day 29 to Month 9). Therefore, the overall fitusiran treatment period is defined as the onset period (Day 1 to Day 28 after receipt of the first dose, during which the AT lowering capacity of fitusiran is increasing but has not yet reached therapeutic levels) plus the efficacy period (Day 29 and after, when the AT lowering capacity of fitusiran has achieved therapeutic target range).

Patients may undergo unplanned or emergency surgery during the study, but must not schedule non-urgent surgery to occur during the study. Perioperative guidance should be followed as specified in Section 6.6.

A Study Steering Committee, composed of experts in the field of hemophilia, will advise the Sponsor on study design and conduct (see Section 4.6).

An independent data monitoring committee (DMC) will oversee the safety and overall conduct of this study as described in Section 4.7.

The study design schema is presented in Figure 1. Patients who complete the study may be eligible for an open-label extension study in which patients coming from both the fitusiran and the on-demand arms will be administered monthly SC doses of fitusiran.

Figure 1: Study Design

Abbreviations: HA/HB = hemophilia type A / hemophilia type B; R = randomized

^a On-demand factor concentrates as routinely prescribed by physician per local standard practice.

^b Fitusiran treatment arm patients who do not enroll in the extension study: AT activity level will be monitored at monthly intervals following the final fitusiran dose until activity levels return to approximately 60% (per the central laboratory) or per Investigator discretion in consultation with the study Medical Monitor.

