6.3.1.2. Bleeding Episode Management Recommendations for Patients in the Fitusiran Treatment Arm

Given the mechanism of action and pharmacodynamic profile of fitusiran, the factor concentrate dose necessary to safely and effectively treat breakthrough bleeding episodes will be lower than standardly prescribed. This is supported by data from the Phase 1 study in which bleed events were managed with factor and BPA, as well as additional modeling and ex vivo spiking data.

More detailed information on the clinical experience in bleeding episode management in Phase 1 and Phase 1/2 fitusiran studies, as well as supportive nonclinical studies is provided in the Investigator's Brochure.

After administration of fitusiran, AT lowering will be progressing toward therapeutic levels. As quickly as 7 days after the initial fitusiran dose, the majority of patients will have AT levels at or below 60% residual activity. By 14 days after dosing, it is expected that 94% of patients will have AT lowering of >50%, with a median value of 66.8 %. Based on these AT kinetics, it is recommended that patients continue with their standard factor regimens for the first 7 days following initiation of fitusiran dosing, with institution of the protocol-specific bleed management guidelines with reduced factor or BPA at Day 8 and beyond ([Table 4](#)).

Patients on fitusiran, will be provided a bleed management plan with appropriate dosing of factor concentrates for use during Day 1 through 7, as well as a bleed management plan with dosing for Day 8 and beyond. Thereafter the bleed management plan will be reviewed and updated at monthly visits, and new written plans provided to the patient if dosing changes.

Importantly, during the treatment period, patients should not use factor concentrates or other hemostatic agents as prophylaxis for bleeding episode prevention, including doses related to anticipated hemostatic challenges such as physical activity. For prophylaxis of bleeding episodes in patients who require operative procedures see [Section 6.6](#).

Bleed Management Guidelines Day 1 to Day 7:

Patients should be instructed to call the site prior to administering factor or BPA. Patients should continue with their standard factor/BPA regimens.

Bleed Management Guidelines Day 8 and Beyond:

When a patient experiences symptoms that may be consistent with bleeding episodes, the following steps should be followed:

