3.2.3 Pharmacodynamic endpoints

- AT activity level over time
- Thrombin generation over time

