6.4.2 Peak thrombin

Peak thrombin values collected within 48 hours of factor, BPA or antifibrinolytic administration will be excluded from all analysis. Peak thrombin values will be summarized descriptively. In addition, MMRM analyses will be performed on change from baseline in peak thrombin with fixed effects of treatment arm, randomization strata of number of bleeding episodes in the

6 months prior to study entry (≤ 10 vs > 10), randomization strata of hemophilia type (A vs B), visit and baseline peak thrombin level. The covariance structure will be chosen to minimize BIC.

Both analyses in AT and peak thrombin may also be performed on a logarithmic scale. The estimates along with 90% confidence intervals will be back transformed to the original scale.

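### The antithrombin and peak thrombin MMRMs have no treatment-by-visit term, so they impose one constant arm difference although antithrombin lowering is expected to be still rising at Day 15

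*SAP*

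**What the plan says.** SAP 6.4.1 plans descriptive summaries of AT and, in addition, an MMRM on AT lowering as a percentage of baseline. Its fixed effects are treatment arm, the prior-bleed stratum, "randomization strata of hemophilia type (A vs B), visit and baseline AT level". SAP 6.4.2 gives change in peak thrombin the same structure, ending with "visit and baseline peak thrombin level". In both, the covariance structure is chosen by BIC. Neither section names an arm-by-visit term, lists the visits that enter the model, or says whether estimates are reported by visit or as one overall contrast.

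The endpoint in SAP 3.2.3 is "AT activity level over time". The expected time course is in the protocol:

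- Section 4.1 describes Days 1 to 28 as a period "during which the AT lowering capacity of fitusiran is increasing but has not yet reached therapeutic levels".
- Section 6.3.1.2 states that by 14 days after dosing "it is expected that 94% of patients will have AT lowering of >50%, with a median value of 66.8" percent.
- Section 1.3 puts the time to reach the target range at about 28 days in most patients.
- Section 1.4 anticipates that "the majority of patients may achieve >75% AT lowering, the therapeutic target".
- Section 1.2.2.3 reports a mean maximal AT reduction of 85.9% on 80 mg in the extension study.

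**The concern.** With main effects only, the visit effect is shared by both arms and the arm effect is one number. The model therefore cannot represent a difference that grows between Day 15 and later visits. On a log scale the same restriction imposes one constant ratio. Yet fitusiran patients are expected to be still moving towards target at Day 15, while on-demand patients receive no AT-lowering drug and should stay near baseline.

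If LS means or differences are reported by visit, the Day 15 difference will be too large and untreated patients will appear to have a rise in AT that did not occur. If one overall contrast is reported, it averages over the onset, with weights that depend on the selected covariance structure. Either way, the model does not describe the time course named in the endpoint.

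For peak thrombin the conflict is indirect. Protocol 1.2.2.3 says that "increased AT lowering in patients with hemophilia resulted in increased thrombin generation when AT lowering was in the highest quartile", so a changing AT difference implies a changing thrombin difference, but no thrombin values by visit are given.

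**Working it through.** The documents state no figure for these models, so there is nothing to reproduce. The check fits the additive model (arm plus visit) by generalised least squares to expected means.

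**Inputs from the documents**
- 80 fitusiran and 40 on-demand patients (protocol 1.3).
- 11 post-baseline visits: Days 15, 29, 43, 57, 85, 113, 141, 169, 197, 225 and 253 (protocol Table 1; the windows in SAP 5.10 match).
- Lowering on fitusiran at Day 15: 66.8%.

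**Assumptions**
- The Day 15 figure is a median, used here as a mean.
- On-demand lowering is 0.
- The fitusiran plateau P from Day 29 is either 75 (the floor of the target) or 85.9 (a mean of individual maxima, so at or above a true plateau mean).
- Data are complete, and strata and baseline are balanced.

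**Formulas.** Let d_t be the true arm difference at visit t and V the within-patient covariance. The fitted constant difference is δ = Σ w_t d_t, with weights w proportional to V⁻¹1 and summing to 1. Writing w₁ for the Day 15 weight:
- δ = P − w₁(P − 66.8)
- Day 15 error = δ − 66.8
- error from Day 29 = δ − P
- fitted on-demand Day 15 mean = (80/120)(66.8 − δ), against a true value of 0

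**Day 15 weight**
- Compound symmetry, any correlation: w₁ = 1/11 = 0.0909.
- Serial correlation of 0.8 per 28 days, hence √0.8 = 0.894 per 14 days, with 3 gaps of 14 days and 7 of 28: w₁ = (1/1.894) / [1 + 3(0.1056/1.894) + 7(0.2/1.8)] = 0.528/1.945 = 0.271.

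**Results (percentage points)**

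| Plateau | Correlation | Constant difference | Day 15 error | Error from Day 29 | On-demand Day 15 mean |
|---|---|---|---|---|---|
| 75 | Compound symmetry | 74.25 | +7.45 | −0.75 | −4.97 |
| 85.9 | Compound symmetry | 84.16 | +17.36 | −1.74 | −11.58 |
| 75 | Serial | 72.77 | +5.97 | −2.23 | −3.98 |
| 85.9 | Serial | 80.72 | +13.92 | −5.18 | −9.28 |

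For example, in row 2: (66.8 + 10 × 85.9)/11 = 925.8/11 = 84.16.

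**Sensitivity.** With Day 29 at 75 and 85.9 thereafter, compound symmetry gives a constant difference of 83.2 and a Day 15 error of 16.4. With a plateau of 87, the Phase 1 mean maximum for 80 mg, the error is (10/11)(87 − 66.8) = 18.4.

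**With the interaction.** Each visit's difference is estimated separately. In one simulated dataset (true differences 66.8 and 85.9, assumed between- and within-patient SD of 6 each), the additive model gave 83.4 at every visit. The interaction model gave 67.8 at Day 15 and 85.1 at Day 253.

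**The case against.** The main objection is about consequence. The SAP does not say that visit-level estimates will come from these models. A single overall contrast would lie within 0.8 to 5.2 points of an assumed plateau difference of 75 to 85.9. Protocol 8.2.6 makes the MMRM optional and has AT and thrombin summarized descriptively by visit, which would show the onset without any model constraint. In the base calculation the error comes entirely from Day 15. If only visits from Day 29 entered the model, it would vanish. The size varies almost threefold with the assumptions, and for peak thrombin there is no size at all.

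Most of this stands as a limit on importance, but it does not remove the problem. Nothing restricts the models to Day 29 onward: Table 1 schedules AT and thrombin generation at Day 15 in both arms, and SAP 5.10 gives that visit its own window. Excluding Day 15 cures the model only if the plateau is already reached by Day 29. With Day 29 at 75 and later visits at 85.9, compound symmetry over the 10 remaining visits leaves a Day 29 error of (9/10)(85.9 − 75) = 9.8 points. Descriptive tables do not correct a model estimate printed beside them. Leaving open whether estimates are overall or by visit is itself something the SAP should settle for an endpoint defined over time.

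**Conclusion.** The concern holds. As written, both MMRMs impose a constant arm difference, and for AT this contradicts the protocol's own expected time course. Under the stated assumptions, by-visit estimates overstate the Day 15 difference by 6.0 to 17.4 points, show 4.0 to 11.6 points of spurious AT rise in untreated patients, and understate the difference from Day 29 by 0.8 to 5.2 points. These sizes rest on a median used as a mean, an assumed plateau, zero change on demand, and inclusion of Day 15. For peak thrombin only the shared model form is established.

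The consequence is limited. These are exploratory pharmacodynamic analyses outside the testing hierarchy, and the primary and secondary efficacy results are unaffected. The change should still be made, because the model misrepresents the feature it is meant to describe and the correction is simple.

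**What to change.** In SAP 6.4.1 and 6.4.2, add a treatment-by-visit interaction to the fixed effects. Name the visits included, and state that LS means and arm differences with intervals will be reported by visit. SAP 6.4.2 already provides for back-transformation with 90% intervals when the log scale is used; say that this applies to the visit-level estimates.

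The cost is SAP wording and (2 − 1) × (11 − 1) = 10 extra fixed-effect parameters per model; no new data are needed. Visit-level intervals are wider than one pooled interval. Under compound symmetry with complete data the width ratio is √[11/(1 + 10ρ)], which is 1.66, 1.35 and 1.11 for within-patient correlations of 0.3, 0.5 and 0.8. For AT this loss is small against an expected difference of about 67 to 86 points.
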